# 4.2.6 Prohibited Therapy

Use of the following therapies is prohibited during the study, unless otherwise specified below:

- Anticholinergic antidepressants, typical antipsychotics, or barbiturates
  - All other antidepressants and atypical antipsychotics are allowed with certain limitations (see Section 4.2.5).

- Anticoagulation medications (e.g., heparin, warfarin, thrombin inhibitors, Factor Xa inhibitors)
  - Clopidogrel, dipyridamole, and aspirin are permitted.
- Any biologic therapy
  - Routinely recommended vaccinations are allowed.
- Any investigational agent

#### 4.3 STUDY ASSESSMENTS

Please see Appendix 1 for the schedule of assessments to be performed during this study.

#### 4.3.1 Informed Consent Forms and Screening Log

Written informed consent for participation in this study must be obtained before performing any study-specific screening tests or evaluations. Informed Consent Forms for enrolled patients and for patients who are not subsequently enrolled will be maintained at the study site.

All screening evaluations must be completed and reviewed to confirm that patients meet all eligibility criteria before enrollment. The investigator will maintain a screening log to record details of all patients screened and to confirm eligibility or record reasons for screening failure, as applicable.

#### 4.3.2 Medical History and Demographic Data

Medical history includes clinically significant diseases, surgeries, reproductive status, smoking history, use of alcohol and drugs of abuse, and all medications (e.g., prescription drugs, over-the-counter drugs, herbal or homeopathic remedies, nutritional supplements) used by the patient at the time of study enrollment on Day 1.

A complete medical history should include a negative or positive history for risk factors for pneumonia including asthma, COPD, heart disease, and smoking; and any other potential risk factor considered significant in the investigator's judgment.

Demographic data will include age, sex, and self-reported race/ethnicity.

# 4.3.3 Physical Examinations

A complete physical examination should include an evaluation of the head, eyes, ears, nose, and throat and the cardiovascular, dermatological, musculoskeletal, respiratory, and gastrointestinal systems. Any abnormality identified at baseline should be recorded on the General Medical History and Baseline Conditions eCRF.

At subsequent visits (or as clinically indicated), changes from baseline abnormalities should be recorded in patient notes. New or worsened clinically significant abnormalities should be recorded as adverse events on the Adverse Event eCRF.

Crenezumab—Genentech, Inc. 49/Protocol GN28525, Version 6

# 4.3.4 Vital Signs

Vital signs will include measurements of heart rate, respiratory rate, temperature, and systolic and diastolic blood pressure after the patient has been supine for  $\geq$ 3 minutes.

#### 4.3.5 Neurologic Examination

A complete neurologic examination should include the evaluation of consciousness, cranial nerves, motor and sensory system, coordination and gait, and reflexes. Changes from baseline abnormalities should be recorded at each subsequent neurologic examination. New or worsened abnormalities should be recorded as adverse events on the Adverse Event eCRF if considered clinically significant in the investigator's judgment.

#### 4.3.6 Magnetic Resonance Imaging Assessments

Neuroradiologic evaluation will be performed using a standard MRI protocol at screening and for routine safety assessments. The MRI protocol will include the following sequences: T1-weighted 3D GRE, dual-echo fast-spin-echo with T2 and proton density weighting (or separate T2-weighted and proton-density-weighted sequences on systems that will not accommodate dual-echo acquisition), T2\*-weighted GRE, and T2-weighted FLAIR. The minimum requirements for T2\*-weighted GRE scans are as follows: field strength of 1.5T or greater, slice thickness of 5 mm or less, and echo time (TE) of 20 ms or greater. Volumetric analysis of the T1-weighted 3D GRE scans is included as an exploratory evaluation of the effect of crenezumab on regional brain volume. All MRIs will be evaluated by a central imaging reader.

# 4.3.7 Columbia-Suicide Severity Rating Scale (C-SSRS)

The Columbia-Suicide Severity Rating Scale (C-SSRS) will be used for prospective suicidality assessment. The C-SSRS is a tool used to assess the lifetime suicidality of a patient and to track suicidal events through the treatment. The structured interview prompts recollection of suicidal ideation, including the intensity of the ideation, behavior, and attempts with actual/potential lethality.

The scale will be administered by qualified site personnel. The C-SSRS "baseline" will be administered at Day 1, and the C-SSRS "since last visit" will be administered at subsequent visits. Patients who are suicidal based on C-SSRS will be referred for appropriate psychiatric evaluation and management as per local clinical practice.

Note: Assessing the risk of suicide is a difficult and complex task when applied to an individual patient. Certainly, no single clinical scale can replace a thorough medical examination and suicide risk assessment. Ultimately, the determination of the presence of suicidality depends on clinical judgment.

# 4.3.8 Neurocognitive and Functional Assessments

In this trial, a number of neurocognitive and functional assessments will be administered, some to the patient and some to the caregiver. In addition, a Caregiver Characterization Questionnaire (CCQ) will be completed prior to the administration of the caregiver assessments at each visit. All neurocognitive and functional assessments are to be performed prior to dosing and any potentially stressful procedures (e.g., blood draws, imaging).

The following assessments will be administered to the patient:

- MMSE
- ADAS-Cog
- CDR (patient portion)
- FCSRT
- TMT
- DST
- DSST
- LFT
- CFT

The following assessments will be administered to the caregiver:

- CCQ
- CDR (caregiver portion)
- ADCS-ADL
- Dependence Scale
- NPI

See Appendix 6 for details regarding the neurocognitive and functional assessments.

#### 4.3.9 Laboratory Assessments

Samples for the following laboratory tests will be sent to one or several central laboratories or to the Sponsor for analysis. Instruction manuals and supply kits will be provided for all central laboratory assessments.

- Hematology: hemoglobin, RBC count, WBC count, and platelets
- Serum chemistry: sodium, potassium, BUN, estimated glomerular filtration rate, aspartate aminotransferase (AST), alanine aminotransferase (ALT), γ-glutamyl transpeptidase, alkaline phosphatase, lactate dehydrogenase, total protein, glucose, cholesterol, triglycerides, and creatine phosphokinase.
- Urinalysis, including dipstick (i.e., pH, specific gravity, glucose, protein, ketones, blood) and microscopic examination (e.g., sediment, RBCs, WBCs, casts, crystals, epithelial cells, bacteria)
- Coagulation: aPTT and INR

**Crenezumab—Genentech, Inc.** 51/Protocol GN28525, Version 6

- Anti-therapeutic antibodies
- PK assessments: blood samples will be collected for measurement of serum crenezumab concentrations to confirm exposure. On dosing days, PK blood samples will be collected prior to study drug administration unless otherwise specified.
- PD assessments: blood samples will be collected from all patients at specified time points for the determination of total plasma Abeta levels as an exploratory measure of PD response to crenezumab treatment. Additional plasma, serum, and RNA samples will be collected from all patients at specified time points to enable exploratory analysis of biomarkers, their response to crenezumab, and their association with clinical efficacy.

On dosing days, PD blood samples will be collected prior to study drug administration, unless otherwise specified.

#### 4.3.10 Electrocardiograms

Single ECG recordings will be obtained at each specified time point (see the schedule of assessments in Appendices 1-3). ECGs acquired on different days should be as closely time-matched as feasible. If possible, ECGs should be recorded on the same type of machine for each site involved in the study, and the same machine should be used for all ECGs for a specific patient.

Lead placement should be as consistent as possible. ECG recordings must be performed after the patient has been resting in a supine position. All ECGs are to be obtained prior to other procedures scheduled at that same time (e.g., vital sign measurements, blood draws). Circumstances that may induce changes in heart rate, including environmental distractions (e.g., television, radio, conversation) should be avoided during the pre-ECG resting period and during ECG recording.

For safety monitoring purposes, the investigator must review, sign, and date all ECG tracings. Paper copies of ECG tracings will be kept as part of the patient's permanent study file at the site.

# 4.4 PATIENT, TREATMENT, STUDY, AND SITE DISCONTINUATION

#### 4.4.1 Patient Discontinuation

Patients have the right to voluntarily withdraw from the study at any time for any reason. In addition, the investigator has the right to withdraw a patient from the study at any time. Reasons for withdrawal from the study may include, but are not limited to, the following:

- Patient withdrawal of consent at any time
- Any medical condition that the investigator or Sponsor determines may jeopardize the patient's safety if he or she continues in the study
- Investigator or Sponsor determines it is in the best interest of the patient

Crenezumab—Genentech, Inc. 52/Protocol GN28525, Version 6

- Patient non-compliance, specifically defined as follows:
  - Patient in the SC cohort misses more than two doses within 6 months
  - Patient in the IV cohort misses more than one dose within 6 months
  - Patients considered non-compliant may need to be withdrawn from the study treatment. Patients should then complete the early treatment discontinuation safety follow-up visit (ET FU Week 8).

Every effort should be made to obtain information on patients who withdraw from the study. Patients who discontinue from the treatment period prior to Week 145 will be asked to return to the clinic within 4 weeks after the last administration of study drug to undergo early termination assessments and should return for additional safety assessments 8 weeks after the early termination assessments. See Appendix 5. The primary reason for withdrawal from the study should be documented on the appropriate eCRF. However, patients will not be followed for any reason after consent has been withdrawn. Patients who withdraw from the study will not be replaced.

# 4.4.2 Study Treatment Discontinuation

Patients with a serious, life-threatening adverse event, superficial siderosis of central nervous system, one new cerebral macrohemorrhage, an increase by one or more in the number of symptomatic cerebral microhemorrhages compared with screening, or an increase by six or more in the number of asymptomatic cerebral microhemorrhages compared with screening, as assessed by T2\*-weighted GRE MRI, must not receive additional doses of crenezumab, and must be discontinued from the study treatment.

The primary reason for study treatment discontinuation should be documented on the appropriate eCRF. Patients who discontinue study treatment prematurely will not be replaced.

#### 4.4.3 Study and Site Discontinuation

The Sponsor has the right to terminate this study at any time. Reasons for terminating the study may include, but are not limited to, the following:

- The incidence or severity of adverse events in this or other studies indicates a potential health hazard to patients.
- Patient enrollment is unsatisfactory.
- Study ABE4689g or ABE4955g is prematurely terminated or fails to demonstrate minimal safety, tolerability, or evidence of activity criteria following completion and evaluation of Study ABE4689g or ABE4955g.

The Sponsor will notify the investigator if the Sponsor decides to discontinue the study.

The Sponsor has the right to close a site at any time. Reasons for closing a site may include, but are not limited to, the following:

- Poor protocol adherence
- Inaccurate or incomplete data recording
- Non-compliance with the International Conference on Harmonisation (ICH) guideline for Good Clinical Practice
- No study activity (i.e., all patients have completed and all obligations have been fulfilled)

#### 5. ASSESSMENT OF SAFETY

#### 5.1 SAFETY PLAN

Crenezumab has not been approved for use by global health authorities and is currently in clinical development. Thus, the entire safety profile is not known at this time. Human experience is currently limited, and the following information is based on results from nonclinical and clinical studies as well as published data on similar molecules. The safety plan for this study is designed to ensure patient safety and will include specific eligibility criteria and monitoring assessments as detailed below.

#### 5.1.1 Amyloid-Related Imaging Abnormalities – Edema/Effusion (ARIA-E)

The occurrence of imaging abnormalities believed to represent cerebral vasogenic edema has been reported in association with the investigational use of compounds that are intended to treat Alzheimer's disease by reducing Abeta in the brain.

These MRI signal hyperintensities seen in the parenchyma and leptomeninges are now more specifically named "amyloid-related imaging abnormalities – edema/effusion" (ARIA-E) to cover the MRI alterations seen in the FLAIR sequence thought to represent edema in the gray and white matter, and effusion or extravasated fluid in the sulcal space (Sperling et al. 2011). These FLAIR signal abnormalities have, in the majority of instances, been asymptomatic, and their presence has been detected by routine brain MRI. Symptoms, when present in association with such imaging abnormalities, have been reported to include headache, worsening cognitive function, alteration of consciousness, seizures, unsteadiness, and vomiting (Sperling et al. 2012; Salloway et al. 2009). The mechanisms underlying ARIA-E observed in these trials are unclear but may at least in part be related to  $Fc\gamma R$  activity of these anti-Abeta antibodies.

When anti-Abeta antibodies bind to amyloid deposited around blood vessels, an  $Fc\gamma R$ -mediated immune response may be elicited, compromising vascular integrity and resulting in ARIA-E. The hypothesis that  $Fc\gamma R$ -mediated immune response may contribute to the occurrence of ARIA-E is supported by results from clinical studies that have shown that up to 17% of the patients treated with anti-Abeta antibodies with full effector function developed ARIA-E that was dependent on the dose level and related to

Crenezumab—Genentech, Inc. 54/Protocol GN28525, Version 6

*ApoE4* status (Sperling et al. 2012). In that study, the mean number of infusions before detection of ARIA-E was 2.4, and most cases of ARIA-E (69%) were identified after the first or second infusion (Sperling et al., 2012).

Crenezumab, a human IgG4, has reduced  $Fc\gamma R$  binding compared with IgG1/2 and thus has reduced effector function that theoretically might lower the risk of ARIA-E.

The potential for improved safety of crenezumab is supported by safety observed in both clinical and nonclinical studies. In the completed Phase I study (ABE4427g), no signs or symptoms of ARIA-E (clinical or radiological) were observed following a single dose of up to 10 mg/kg or four weekly doses of up to 5 mg/kg. In the completed Phase II Studies ABE4869g and ABE4955g, a single case of ARIA-E has been observed (see above), supporting the reduced risk of developing ARIA-E with crenezumab. The very low rate of ARIA-E in Studies ABE4869g and ABE4955g supports a reduced frequency of brain MRIs (every 6 months vs. 3 months) in this study. For additional details on clinical studies, see the Investigator's Brochure.

In this OLE study, the following safety monitoring plan has been designed to mitigate and monitor the potential risk of cerebral ARIA-E:

- Patients included in the study will regularly undergo neurologic examinations to evaluate for any neurologic signs or symptoms that are suggestive of the presence of ARIA-E (e.g., confusion, dizziness, vomiting, lethargy).
- Brain MRI (including FLAIR) will be performed at least every 6 months to detect non-symptomatic ARIA-E.
- All MRIs will be read in real time for the evaluation of ARIA-E by independent radiologists at a central contract imaging reader. Study drug will be held if MRI abnormalities consistent with ARIA-E appear.
- Patients who exhibit ARIA-E as assessed by FLAIR MRI will not receive additional study drug until the investigator has determined that ARIA-E has resolved (as assessed by short-interval MRI and clinical evaluation). Treatment with high-dose dexamethasone should be considered if symptoms of ARIA-E are severe.
- Regardless of severity, all events of ARIA-E that occur at any time after receiving study drug are considered to be adverse events of special interest and will be reported in an expedited manner (see Section 5.2.3).

# 5.1.2 Amyloid-Related Imaging Abnormalities–Hemorrhage (ARIA-H)

Cerebral microhemorrhages (microbleeds [MBs]) are radiologically defined as small dot-like foci of signal loss observed on MRI sequences sensitive for paramagnetic tissue properties (i.e., T2\*-weighted or SWI) (Greenberg et al. 2009). This signal loss is caused by residual blood breakdown products, hemosiderin, or iron stored in macrophages in the brain parenchyma around damaged small vessels. The most common causes for this small vessel damage and subsequent leakage are hypertensive vasculopathy and CAA. CAA is believed to predominantly cause MBs in Alzheimer's disease (Cordonnier et al. 2011).

MBs in Alzheimer's disease have a point prevalence of 23% (Cordonnier et al. 2011). One longitudinal study found that in Alzheimer's disease patients the incidence of one or more MBs after a mean follow-up of 2 years was 12% (Goos et al. 2010). Recently, the occurrence of MBs has also been identified as an adverse event in anti-amyloid vaccination trials, and together with superficial siderosis, they have been termed "amyloid-related imaging abnormalities-hemorrhage (ARIA-H) (Sperling et al. 2011). Limited data on ARIA-H occurrence is available, but a recent retrospective analysis in Alzheimer's disease patients treated with anti-Abeta antibodies with full effector function reported that 24 out of 207 participants (11.6%) developed ARIA-H (Sperling et al. 2012). Acute occurrence of MBs is not considered clinically symptomatic (Greenberget al., 2009). In fact, study patients who received active drug and developed ARIA-H without ARIA-E were all clinically asymptomatic (Sperling et al. 2012).

In the *completed* Phase II studies ABE4869g and ABE4955g, patients underwent an MRI assessment at least every 3 months that included a T2\*-weighted sequence; new MBs were detected in 11.6% of patients receiving crenezumab and 12.5% of patients receiving placebo. For additional details on clinical studies see the Investigator's Brochure.

In this OLE study, the following safety monitoring plan has been designed to mitigate and monitor the potential risk of cerebral ARIA-H:

- Patients with superficial siderosis of central nervous system, more than eight cerebral microhemorrhages, or evidence of a prior cerebral macrohemorrhage (as assessed by a central reader based on T2\*-weighted GRE MRI) will be excluded from the trial.
- Brain MRIs (T2\*-weighted GRE sequences) will be performed at least every 6 months to detect superficial siderosis of central nervous system, and cerebral micro- or macrohemorrhages.

- All MRIs will be read in real time for the evaluation of ARIA-H by independent radiologists at a central contract imaging reader. Study drug will be discontinued if patients who exhibit superficial siderosis of central nervous system, one new cerebral macrohemorrhage, an increase by one or more in the number of symptomatic cerebral microhemorrhages compared with screening, or an increase by six or more in the number of asymptomatic cerebral microhemorrhages compared with screening.
- Patients who exhibit new asymptomatic cerebral microhemorrhages, but do not qualify for treatment discontinuation as defined above, will be re-scanned within 8 weeks after the last MRI scan to evaluate their stability.
- Regardless of severity, all events of ARIA-E that occur at any time after receiving study drug are considered to be adverse events of special interest and will be reported in an expedited manner (see Section 5.2.3).

#### 5.1.3 Pneumonia

As described in Section 1.3.3, in the RPCP of Phase II clinical trials in mild-to-moderate Alzheimer's disease (ABBY and BLAZE), there was an imbalance in the rates of pneumonia, with 3.2% (11/346) of crenezumab-treated patients and 0.6% (1/176) of patients on placebo having pneumonia. Of these 12 pneumonia cases, 7 were assessed as serious (4 on crenezumab IV, 2 on crenezumab SC, and 1 on placebo).

The rate of pneumonia in crenezumab-treated patients (3.2%) is within the reported incidence of pneumonia in the elderly population (2.5%-4.4%) (Chong et al. 2008), but rates (both total and serious) are slightly higher in crenezumab-treated patients (3.2%) and slightly lower in placebo-treated patients (0.6%) than rates reported in the active and placebo arms of clinical trials in Alzheimer's disease (Doody et al. 2014; Henley et al. 2014; Salloway et al. 2014). There is no clinical evidence of immunosuppression (e.g., effects on white blood cells or neutrophils; or pattern of infection type, e.g., opportunistic infections). In addition, no evidence of immunosuppression or of a lung toxicity effect has been observed in preclinical studies. Based on the currently available data, a causal relationship between the drug and events of pneumonia cannot be established or ruled-out. Pneumonia is considered a potential risk and will be monitored closely.

Pneumonia is now considered an adverse event of special interest and should be reported in an expedited manner (see Section 5.2.3).

Patients with signs and/or symptoms suggestive of pneumonia (e.g., cough, fever, pleuritic chest pain) should undergo chest radiography for confirmation of diagnosis. Additional tests might be considered at the discretion of the treating physician. Patients should be treated as per the standard treatment of care, and any change to study drug should be considered within a benefit/risk assessment frame and be in agreement with the Medical Monitor.

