### 1.3.3.4.2 Pneumonia and Other Lower Respiratory Tract Infections

In the RPCP of Phase II clinical trials in mild-to-moderate Alzheimer's disease (ABE4869g and ABE4955g), there was an imbalance in the overall rates of pneumonia *(including serious and non-serious)*, with 3.2% (11/346) of crenezumab-treated patients and 0.6% (1/176) of patients receiving placebo *experiencing* pneumonia. Of these 12 pneumonia cases, 7 were assessed as serious *(in 4 patients* receiving crenezumab IV, 2 *patients* receiving crenezumab SC, and 1 *patient* receiving placebo).

The rate of pneumonia in crenezumab-treated patients (3.2%) is within the reported incidence of pneumonia in the elderly population (2.5% - 4.4%) (Chong et al. 2008), but rates (both total and serious) are slightly higher in crenezumab-treated patients (3.2%) and slightly lower in placebo-treated patients (0.6%) than rates reported in the active and placebo arms of clinical trials in Alzheimer's disease (Doody et al. 2014; Henley et al.

Crenezumab—Genentech, Inc. 33/Protocol GN28525, Version 6

2014; Salloway et al. 2014). There is no clinical evidence of immunosuppression (e.g., effects on white blood cells or neutrophils; or pattern of infection type, e.g., opportunistic infections). In addition, no evidence of immunosuppression or of a lung toxicity effect has been observed in preclinical studies. Based on the currently available data, a causal relationship between the drug and events of pneumonia cannot be established or ruled out. Pneumonia is considered a potential risk to be monitored closely, and is added to this protocol as an adverse event of special interest.

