## 1.3.6 Benefit-Risk Summary

The safety and tolerability of crenezumab in humans has been assessed in 540 patients exposed to crenezumab in six studies (two Phase I and four Phase II) that showed an acceptable safety profile. Details are provided above and in the crenezumab Investigator's Brochure.

Clinical experience to date has not identified any events considered to be adverse drug reactions (i.e., a drug causality link has not been established with any of the reported adverse events). Potential safety considerations associated with treatment include those inherent to recombinant protein therapeutics as well as those specific to the crenezumab molecule or pharmacology. These include pneumonia, the spectrum of potential immune-mediated responses (e.g., hypersensitivity reactions, anaphylaxis), immunogenicity (anti-drug antibody formation), cerebral vasogenic edema/sulcal effusion, cerebral micro-/macro-hemorrhages, and superficial siderosis. Given the imbalances observed in pneumonia reports between crenezumab and placebo during the RPCP of the Phase II program, pneumonia is now considered a new potential risk for crenezumab treatment.

Given the early stage of development, the long-term safety profile of crenezumab in humans has not yet been fully characterized. Therefore, not all of the potential adverse effects, and the likelihood of their occurrence, are known at this time. Patients will continue to be carefully monitored throughout the clinical development of crenezumab to collect additional safety information.

This OLE study will permit the evaluation of long-term safety and tolerability of crenezumab in patients who completed the Week 73 assessment in Study ABE4869g or ABE4955g. In addition, this OLE study will provide the opportunity for eligible patients treated with placebo in Studies ABE4869g and ABE4955g to continue into the OLE and receive crenezumab.

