## 3.4 OUTCOME MEASURES

## 3.4.1 Primary Outcome Measures

Safety and tolerability will be assessed through regular neurologic and physical examinations and MRI assessments. In addition, the following information will be collected and analyzed:

- Frequency of adverse events during the treatment period
- Nature and severity of adverse events during the treatment period
- Changes in vital signs and physical and neurological findings
- Changes in clinical laboratory test results including routine hematology, chemistry, coagulation, and urinalysis
- Incidence of human anti-therapeutic antibody (ATA) formation
- Incidence of ARIA-E and amyloid-related imaging abnormalities-hemorrhage (ARIA-H)

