# 5.1.4 Deaths

As described in Section 1.3.3, in the RPCP of the Phase II clinical trials in mild-tomoderate Alzheimer's disease (ABBY and BLAZE), there were 5 deaths. All 5 deaths occurred in patients treated with crenezumab, and none were assessed as related to study drug by the investigator. This represents 1.4% (5/346) of patients receiving crenezumab compared with 0.0% (0/176) of patients receiving placebo. The causes of death are in line with published literature showing no prevalent cause of death among Alzheimer's disease treatment trials (Henley et al. 2012; Henley et al. 2014; Doody et al. 2014).

A causal relationship between crenezumab and the fatal events cannot be established or ruled out. Fatal events will continue to be monitored closely for the identification of any potential pattern (e.g., a more frequent cause of death) or a particular population group at risk (e.g., gender, age group, particular comorbidity). Exposure-adjusted rates will be assessed and compared with published background rates from a similar study population (Henley et al. 2012; Henley et al. 2014).

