#### 5.2.3 Non-Serious Adverse Events of Special Interest (Immediately Reportable to the Sponsor)

Non-serious adverse events of special interest are required to be reported by the investigator to the Sponsor immediately (i.e., no more than 24 hours after learning of the event; see Section 5.4.2 for reporting instructions). Adverse events of special interest for this study include the following:

• Cerebral vascular edema (ARIA-E)

Crenezumab—Genentech, Inc. 59/Protocol GN28525, Version 6

- Superficial siderosis of central nervous system (ARIA-H)
- Cerebral microhemorrhages (ARIA-H) or macrohemorrhages
- Occurrence of pneumonia regardless of severity/seriousness or relatedness with study drug. Diagnosis is to be verified by imaging (e.g., chest X-ray) (see Sections 3.4.3 and 5.1.3)
- Suspected transmission of an infectious agent by the investigational product, as defined below:

Any organism, virus, or infectious particle (e.g., prion protein transmitting transmissible spongiform encephalopathy), pathogenic or non-pathogenic, is considered an infectious agent. A transmission of an infectious agent may be suspected from clinical symptoms or laboratory findings that indicate an infection in a patient exposed to a medicinal product. This term applies only when a contamination of the study drug is suspected.

• Cases of potential drug-induced liver injury that include an elevated ALT or AST in combination with either an elevated bilirubin or clinical jaundice, as defined by Hy's law (see Section 5.3.5.6)

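### Pneumonia was made an event of special interest after a feeder-study imbalance, but unlike deaths it has no planned exposure-adjusted rate, so OLE frequencies cannot be read against the feeder percentages

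*Combined protocol and SAP*

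**What the plan says.** Section 5.1.3 gives the feeder result as "3.2% (11/346) of crenezumab-treated patients and 0.6% (1/176) of patients on placebo having pneumonia"; of the 12 cases, "7 were assessed as serious (4 on crenezumab IV, 2 on crenezumab SC, and 1 on placebo". Section 1.3.6 concludes that "pneumonia is now considered a new potential risk for crenezumab treatment", and Section 1.3.3.4.2 that "a causal relationship between the drug and events of pneumonia cannot be established or ruled out". Pneumonia was therefore added as an adverse event of special interest, with 24-hour reporting and verification by imaging (Sections 5.1.3 and 5.2.3). Section 5.1.3 then states "Pneumonia is considered a potential risk and will be monitored closely" and gives reporting and diagnostic steps, but no analysis.

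The primary outcomes in Section 3.4.1 cover adverse events generally (frequency, nature, severity). They name one pair of special-interest events, "Incidence of ARIA-E and amyloid-related imaging abnormalities-hemorrhage (ARIA-H"). Pneumonia is not named. Its entry in Section 5.2.3 directs the reader to "see Sections 3.4.3 and 5.1.3", but both the contents list and the body stop at Section 3.4.2.

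Section 6.4 groups patients by OLE treatment and feeder assignment. Section 6.4.1 summarises coded adverse events separately for screening, the 144-week treatment period and the 8-week follow-up. Sections 6.4.2 to 6.4.4 deal with laboratory data, MRI and anti-therapeutic antibodies. No subsection gives a person-time denominator or a comparator for pneumonia.

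Deaths are treated differently. Section 5.1.4 says "Exposure-adjusted rates will be assessed and compared with published background rates from a similar study population", and Section 1.3.3.5 makes a similar commitment for fatalities, using total person-time on crenezumab.

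**The concern.** Section 1.3.3.5 names deaths and pneumonia together as imbalances for which a causal link has not been established. Only deaths get a rate that accounts for time at risk, and no reason is given for the difference.

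The omission matters because follow-up is unequal. Feeder treatment ran for up to 68 weeks. The OLE first planned 92 weeks of treatment and now plans 144, and patients who had already completed or discontinued cannot enter the extension (Section 3.1.1). OLE exposure will therefore vary widely between patients. A percentage of patients with pneumonia mixes the rate with the length of observation, and readers will naturally set it beside the 3.2% and 0.6% in the protocol. They could be falsely alarmed by long follow-up or falsely reassured by early withdrawal.

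**Working it through.** **1. Reproduce the protocol's figures.** 11/346 = 3.18% and 1/176 = 0.57%, matching 3.2% and 0.6%. The counts agree with Section 1.3.3.3: 6 serious + 5 non-serious = 11 on crenezumab; 1 + 0 = 1 on placebo.

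**2. Compare the two imbalances (Fisher exact, two-sided).**

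| Event | Crenezumab | Placebo | p |
|---|---|---|---|
| Pneumonia, all | 11/346 | 1/176 | 0.068 |
| Pneumonia, serious | 6/346 | 1/176 | 0.43 |
| Death | 5/346 | 0/176 | 0.17 |

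For all pneumonia the risk difference is 2.6 points (Newcombe 95% CI -0.3 to 5.1). The evidence is not conclusive, but it is no weaker than for deaths, which have the fuller plan.

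**3. Feeder rates per person-time.** Assume every patient had the full 68 weeks. This is the longest treatment time the protocol allows, so true rates over treated time would be somewhat higher.
- Crenezumab: 346 × 68/52 = 452 patient-years; 11/452 = 2.43 per 100 (exact 95% CI 1.21 to 4.35).
- Placebo: 176 × 68/52 = 230 patient-years; 1/230 = 0.43 per 100 (exact 95% CI 0.01 to 2.42).
- Rate ratio: 2.43/0.434 = 5.6 (exact conditional 95% CI 0.8 to 241).

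**4. What duration does to a crude percentage.** With a constant rate of 0.0243 per year, the expected percentage with a first event is 1 - exp(-0.0243 × weeks/52):
- 68 weeks: 3.1%
- 92 weeks: 4.2%
- 144 weeks: 6.5%

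The percentage doubles with no change in risk. Conversely, 3.2% of patients over a mean of 144 weeks is 3.18/(144/52) = 1.15 per 100 patient-years, less than half the feeder rate, yet it would look identical to the feeder figure.

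**5. What the placebo-origin patients could show.** The percentages in Section 1.3.3.5 imply 148 SC and 211 to 213 IV patients, about 360 in all. If the feeder placebo share carries over (an assumption), 360 × 176/522 = 121 are placebo-origin. Events expected on drug in the OLE:
- Full 144 weeks (121 × 144/52 = 335 patient-years): 8.1 at the feeder crenezumab rate, 1.5 at the placebo rate.
- Half of that (mean 72 weeks, 168 patient-years): 4.1 and 0.7.

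Their placebo period is 121 × 68/52 = 158 patient-years, with 0.7 events expected at the placebo rate.

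The exact conditional test of on-drug against off-drug rates takes the OLE events, given the total, as binomial with null probability t_OLE/(t_OLE + t_feeder), and rejects when the upper tail is at most 0.025. Averaged over Poisson totals at the observed rate ratio of 5.6, power is 13.4% at 72 weeks and 16.5% at 144 weeks. The same calculation for 120 to 130 patients and mean follow-up of 68 to 153 weeks stays between about 11% and 23%. Eight OLE events against one feeder event would give a two-sided p of about 0.3.

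**The case against.** Much of the safety apparatus is in place. Pneumonia falls under the primary outcome of adverse-event frequency, so a reader who infers that no primary outcome covers it goes too far. A reader might also infer that the plan yields one pooled count with everyone on drug. Section 6.4 rules that out: grouping by feeder assignment lets crude frequencies be shown separately for placebo-origin and active-origin patients. Nor was the OLE designed to follow pneumonia. Its objective is general long-term safety (Section 2), and pneumonia was added by amendment. Section 3.1.2 provides periodic safety review, Section 4.3.2 collects pneumonia risk factors, and Section 5.7 has the sponsor compare cumulative event frequency with the Investigator's Brochure.

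These points stand and narrow the gap, but none of them supplies a person-time rate.

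A further tempting inference is that placebo patients crossing to drug would settle whether pneumonia follows crenezumab. They would not. The off-drug rate rests on one event, and its upper limit (2.42) reaches the crenezumab point estimate (2.43). Section 5.1.3 itself calls the placebo rate slightly lower than in other Alzheimer's trials, so some rise towards background is likely without any drug effect. If the true background were 1.2 or 2.0 per 100 patient-years (assumed values), five or more events in 335 patient-years would occur with probability 37.5% or 80%. The contrast is also confounded by ageing, disease progression, and the change to expedited reporting with imaging verification. OLE entrants are selected too, since they must have completed Week 73. Active-origin patients passed the same selection, so they are only an imperfect check on drift. Serious pneumonia is probably less sensitive to the reporting change, but has fewer events.

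Finally, Section 6.7 refers exploratory analyses to a statistical analysis plan whose text is not available here. Absence can be claimed only for the text supplied.

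**Conclusion.** The point holds as a gap in how pneumonia is to be summarised. The protocol applies an exposure-adjusted rate with an external reference to deaths, but not to pneumonia, which it regards as a new potential risk and for which the feeder imbalance was at least as marked (p = 0.068 against 0.17). With follow-up of up to 68 weeks in one period and up to 144 in the other, crude percentages can differ twofold at the same underlying rate. The planned frequencies therefore cannot be compared with the feeder figures. The broken reference to Section 3.4.3 is a plain error.

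The remedy gives an interpretable estimate, not a test of causality. Power of about 13% to 17% for the placebo-origin contrast assumes 121 such patients, mean OLE follow-up of 72 to 144 weeks, full 68-week feeder exposure and the observed rate ratio. The change is worth making because it is cheap; its absence does not undermine the study's general safety objective.

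**What to change.** - **Section 6.4.1:** report total and serious pneumonia per 100 patient-years with exact 95% confidence intervals, by feeder assignment (placebo-origin, active-origin) and by period (feeder, OLE), using the same OLE entrants in both periods. Define time at risk for each period.
- **External reference:** set the rates beside a published background rate from a similar population, chosen in advance, as is already planned for deaths.
- **Section 3.4.1 (and the synopsis):** name pneumonia incidence alongside ARIA-E and ARIA-H.
- **Section 5.2.3:** correct or remove the reference to Section 3.4.3.
- **Interpretation:** state that the table is descriptive, with no hypothesis test, and list the limits: few events, ageing, disease progression, changed reporting and imaging verification, and selection of Week 73 completers.

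The cost is one outcome line, one corrected reference and one table. It needs no new assessments, but feeder adverse-event and exposure records must be linked to the OLE data. The main risk is over-reading small counts, which the intervals and the descriptive label should limit.
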